PASS information

Title	A pharmacoepidemiological study of rivaroxaban use and potential adverse outcomes in routine clinical practice in the Netherlands
Protocol version identifier	5.2
Date of last version of protocol	20 Jan 2015
EU PAS register number	Study to be registered after PRAC approval
Active substance	B01AF01 Antithrombotic agents, direct Factor Xa Inhibitors, Rivaroxaban
Medicinal product	Xarelto
Product reference	Bay59-7939
Procedure number	EMA/H/C/00944
Marketing authorization holder(s)	Bayer Pharma AG, D-13353 Berlin, Germany
Joint PASS	No
Research question and objectives	
To assess patterns of drug utilization and to quantify outcomes related to safety and effectiveness in new users of rivaroxaban compared with new users of standard of care in routine clinical practice in the Netherlands.
 
To provide a description of patients who are prescribed oral rivaroxaban for the first time in comparison with those who are prescribed standard of care for the first time, and describe the characteristics of rivaroxaban use (including indication, dose and duration).
 
To determine time-trends in the characteristics of first-time use of rivaroxaban.
 
To study the occurrence of hospitalization for three bleeding events (primary safety outcomes): intracranial haemorrhage, gastrointestinal bleeding and urogenital bleeding among users of rivaroxaban (for the treatment of deep vein thrombosis [DVT] or pulmonary embolism [PE] and prevention of recurrent DVT and PE, stroke prevention in atrial fibrillation and prevention of atherothrombotic events following an acute coronary syndrome) in comparison with individuals receiving

	
current standard of care.
 
Secondary objectives: to study the occurrence of other bleeding events leading to hospitalization, non-infective liver disease (secondary safety outcomes) and to study outcomes related to effectiveness (DVT/PE, ischaemic stroke and myocardial infarction) and all-cause mortality.

Country(-ies) of study	The Netherlands
Author	
[name] [name]
 
PHARMO Institute for Drug Outcomes Research, Utrecht, The Netherlands

Marketing authorization holder

Marketing authorization holder(s)	Bayer Pharma AG, D-13353 Berlin, Germany
MAH contact person	[name]

The study will be conducted in compliance with the protocol and any applicable regulatory requirements.

VTE	Venous thromboembolism

3 Responsible parties

Principal investigators: [name] [name]

PHARMO Institute for Drug Outcomes Research, Utrecht, The Netherlands

Qualified Person for Pharmacovigilance: [name]

Bayer Pharma AG, D-13353 Berlin, Germany.

4 Abstract

A pharmacoepidemiological study of rivaroxaban use and potential adverse outcomes in routine clinical practice in the Netherlands

Version 5.2, 20 Jan 2015

[name] [name]

PHARMO Institute for Drug Outcomes Research, Utrecht, The Netherlands

Rationale and background

Rivaroxaban is an oral, direct Factor Xa inhibitor with multiple indications, including: treatment of deep vein thrombosis (DVT) and pulmonary embolism (PE) and prevention of recurrent DVT and PE (DVT/PE treatment); stroke prevention in atrial fibrillation (SPAF); and prevention of atherothrombotic events (when combined with antiplatelet therapy) following an acute coronary syndrome (ACS). The use of anticoagulants is associated with the risk of bleeding, and monitoring of the safety profile and patterns of rivaroxaban use in routine care is required. This study in the Netherlands forms part of a post-authorization safety study programme in several European countries.

Research question and objectives

To provide a detailed description of patients who are prescribed oral rivaroxaban for the first time in comparison with those who are prescribed standard of care for the first time, and describe the characteristics of rivaroxaban use (including indication, dose and duration of treatment). To determine time-trends in the characteristics of first-time use of rivaroxaban. Primary safety outcomes are the occurrence of hospitalization for intracranial haemorrhage, gastrointestinal bleeding or urogenital bleeding, among users of rivaroxaban in comparison with individuals receiving current standard of care.

Study design

This study has a cohort design.

Population

Study drug users will be selected from the outpatient pharmacy database in the PHARMO Database Network. All patients aged 2 years and above who have been registered in the database for at least 1 year before the index date will be included. For part of this population, data from General Practice is available which is crucial for the assignment of the indication of use.

Variables

Detailed descriptive variables will be captured for the population, including co-medications. Primary safety outcomes are the occurrence of hospitalization for intracranial haemorrhage, gastrointestinal bleeding and urogenital bleeding. Other outcomes of interest include hospitalization for bleeding events not defined in the primary outcome (other bleeding), non-infective liver disease, outcomes related to effectiveness (DVT/PE, ischaemic stroke, myocardial infarction), and all-cause mortality.

Data sources

Data will be obtained from a linked cohort created using the PHARMO Database Network. The PHARMO Database Network is a population-based network of healthcare databases and combines data from different healthcare settings in the Netherlands.

Study size

The size of the population receiving rivaroxaban will be dependent on market uptake. Based on an incidence of haemorrhagic stroke in vitamin K antagonist-treated patients of 5 per 1000 person-years, 12,000 rivaroxaban-treated patient-years and 48,000 vitamin K antagonist-treated patient-years would be required to exclude a 50% increased risk of haemorrhagic stroke in rivaroxaban-treated patients compared with vitamin K antagonist-treated patients, with a power of 80%.

Data analysis

The patient populations will be described according to the descriptive variables, overall and stratified by indication where possible (VTE prevention, DVT/PE treatment, SPAF, ACS, other), naïve or non-naïve status, and switching status. Age- and sex-adjusted odds ratios and 95% confidence intervals (CI) for the descriptive variables, will be computed using logistic regression models both overall and stratified by indication and by naïve or non-naïve status, and switching status.

Crude incidence rates for the safety and effectiveness outcomes will be estimated in the cohorts for DVT/PE treatment, SPAF and ACS. Incidence will be computed using the person–time contribution of the study cohorts, stratified into current, recent, past and non-use.

Age- and sex-adjusted rate ratios with 95% CIs will be estimated for each of the three primary adverse outcomes comparing rivaroxaban with standard of care using Poisson regression analysis based on person–time contribution.

Milestones

Data collection will start from 10 December, 2011 (day after rivaroxaban received marketing authorization for DVT treatment in the Netherlands) and finish on 31 December, 2018.

5 Amendments and updates

Table 1: Amendments

Number	Date	Section of study protocol	Amendment	Reason
6	Jan 2015	9.3.2.1 9.7.2 9.7.2.1	Addition to section on bleeding definition Addition to section on renal failure definition Addition of section to handle missing data	Response to PRAC review
5	Nov 2014	8.2 9.3.1 9.7.1 9.7.2.1 Annex 3	Additional variables for patient characterisation and analyses thereof; strengthened analyses of renal impairment. Table 12, ICD codes related to renal impairment added	Response to PRAC review
4	May 2014	General	Extension of study timelines. Comparator updated for acute coronary syndromes. Added secondary safety outcome: "other bleeding" Transfer to EMA protocol template. Label wording updated. Current protocol is V5.0.	PRAC request
3	Mar 2012		Inclusion of additional indication, treatment of pulmonary embolism. V4.0 of protocol.	Label expansion
2	Dec 2011		Inclusion of additional indication, acute coronary syndrome. V3.0 of protocol submitted with EU RMP V	Label expansion

			7.1	
1	Apr 2011		Inclusion of additional indication, stroke prevention in atrial fibrillation. V2.0 of protocol submitted with EU RMP V 6.1.	Label expansion

6 Milestones

Table 2: Milestones

Milestone	Planned date
Start of data collection (Marketing Authorization granted for DVT treatment)	Q1 2012
Interim report 1 2 years drug utilization data and crude incidences for primary safety outcomes	Q4 2015
Interim report 2 4 years drug utilization data and crude incidences for primary safety outcomes	Q4 2017
End of data collection	Q4 2018
Final data availability	Q4 2019
Progress reports	Annual in November 2014–19
Final report of study results with full outcomes analysis	Q4 2020
Registration in the EU PAS register	Study to be registered after PRAC approval

7 Rationale and background

Rivaroxaban, a direct Factor Xa inhibitor, is licensed for multiple indications:

- The treatment of deep vein thrombosis (DVT) or pulmonary embolism (PE), and prevention of recurrent DVT and PE in adult patients (DVT/PE treatment) (15 mg rivaroxaban twice daily [bid] for 3 weeks, then 15 mg or 20 mg once daily [od]).
- The prevention of stroke and systemic embolism in adult patients with non-valvular atrial fibrillation (stroke prevention in atrial fibrillation [SPAF]) with one or more risk factors, such as congestive heart failure, hypertension, age \geq 75 years, diabetes mellitus, prior stroke or transient ischaemic attack (20 mg rivaroxaban od).
- The prevention of venous thromboembolism (VTE) in adult patients undergoing elective hip or knee replacement surgery (recommended dose: 10 mg rivaroxaban od for 35 days following hip replacement surgery and 14 days following knee replacement surgery).
- Co-administered with acetylsalicylic acid (ASA) alone or with ASA plus clopidogrel or ticlopidine, for the prevention of atherothrombotic events in adult patients after an acute coronary syndrome (ACS) with elevated cardiac biomarkers (recommended dose 2.5 mg bid).

As is the case with other anticoagulants, clinical studies of rivaroxaban have identified haemorrhage as an important safety outcome ([Lassen et al. 2008](#); [Turpie et al. 2009](#)). A post-authorization safety study programme is planned for several European countries. The aim of this document is to summarize the design of a population-based study to characterise new users of rivaroxaban, assess patterns of drug utilization, including adherence to label recommendations, and to assess the risk of bleeding associated with rivaroxaban treatment in comparison with treatment with standard of care, in routine clinical practice in the Netherlands, for DVT/PE treatment, SPAF and ACS. For DVT/PE treatment and SPAF, standard of care is treatment with a vitamin K antagonist (acenocoumarol or phenprocoumon), and for the secondary prevention of ACS, standard of care is antiplatelet drug(s) such as low-dose acetylsalicylic acid, clopidogrel, dipyridamole, prasugrel, ticlopidine and ticagrelor. The standard of care treatments for ACS will require at least dual antiplatelet and be analysed as combination treatment, irrespective of the individual drug combinations used.

8 Research questions and objectives

This post-authorization study was designed to assess patient characteristics and patterns of drug utilization and to quantify outcomes related to safety and effectiveness in new users of rivaroxaban compared with new users of standard of care.

8.1 Primary objective

8.1.1 Patient characteristics and drug utilization

- To provide a description of patients who are dispensed oral rivaroxaban for the first time in comparison with those who are dispensed standard of care for the first time, and describe the characteristics of rivaroxaban use (including dose and duration).

- To determine time-trends in the characteristics of first-time use of rivaroxaban.

8.1.2 Safety and effectiveness outcomes

- To study the occurrence of hospitalization for three bleeding events (primary safety outcomes): intracranial haemorrhage, gastrointestinal bleeding and urogenital bleeding among users of rivaroxaban (for VTE treatment, SPAF and ACS) in comparison with individuals receiving standard of care.

8.2 Secondary objective(s)

- To study the occurrence of hospitalization for bleeding events not specified as primary safety outcomes (“other bleeding”) in comparison with individuals receiving current standard of care (secondary safety outcome).
- To study the occurrence of non-infective liver disease (secondary safety outcome).
- To study outcomes related to effectiveness (DVT/PE, ischaemic stroke, myocardial infarction).
- To study all-cause mortality.
- To conduct sub-group analysis of safety and effectiveness outcomes in populations of special interest:
 - patients with decreased renal function
 - elderly patients
 - patients with cardiovascular comorbidities e.g. hypertension or diabetes.

9 Research methods

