9.3 Variables

9.3.1 Patient characteristics and drug utilization

Descriptive variables of drug utilization will be presented only for the subpopulation captured by both the outpatient pharmacy database and the GP database, as only in this subpopulation sufficient information for the assignment of the indication of use is available. The following characteristics, including risk factors/potential confounders for the outcomes under study, will be presented for comparison between the two cohorts:

- age and sex distribution at index date 
- dose of index drug at index date (not available for vitamin K antagonists as dosing is determined in anticoagulation clinics) 

- dispensed amount (can be used to estimate duration of treatment) ✓
- where available based on hospital discharge diagnosis or from available GP notes, diagnosis associated with the prescribing of the index drug (where not available, dose and duration of index drug will be used as a proxy for the associated diagnosis among rivaroxaban users). Hospital discharge diagnoses and procedures will be identified within 4 weeks before until 7 days after the index date and GP diagnosed will be identified during the index month or in the month before the index date.
- proportion of patients defined as naïve, non-naïve, recent switchers and distant switchers ✓
- number of pregnant women at index date (if communicated by midwife or gynaecologist) ✓
- number of pregnancies after index date (if communicated by midwife or gynaecologist) ✓
- type of other anticoagulant use before the index date among the non-naïve group ✓
- use of specific prescribed medications both in the year before the index date and following the index date, confirming the ACS indication: antiplatelet drugs (low-dose acetylsalicylic acid, clopidogrel, dipyridamole, prasugrel, ticlopidine and ticagrelor); ✓

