- use of other medications both in the year before the index date and following the index date: anticoagulants (including dabigatran etexilate and apixaban), antiarrhythmic drugs, antihypertensive drugs, statins, anti-diabetic agents, non-steroidal anti-inflammatory drugs, oral corticosteroids, acid-suppressive drugs, disease-modifying anti-rheumatic drugs, antidepressants, antipsychotic drugs, oral contraceptives, hormone-replacement therapy, strong inhibitors of either cytochrome P450 3A4 or P-glycoprotein (e.g. the systemic azole antimycotics ketoconazole, itraconazole, voriconazole and posaconazole and the HIV-protease inhibitor ritonavir), strong CYP3A4 inducers (e.g. rifampicin, phenytoin, carbamazepine or phenobarbital) and fluconazole. ✓
- renal status (estimated glomerular filtration rate [eGFR] or creatinine clearance [CrCl] to be obtained where available, and time of measurement relative to index date). Renal status to be defined as: normal renal function (CrCl > 80 mL/min); mild (CrCl < 80–50 mL/min), moderate (CrCl < 50–30 mL/min) or severe (CrCl < 30 mL/min) renal impairment and end-stage renal disease (CrCl < 15 mL/min) or requirement for dialysis). ✓
- smoking status and body mass index (BMI) recorded in the year before the index date and following the index date.
- hospital admissions for bleeding (see ICD-9 codes in Annex 3) in the year before the index date.
- healthcare utilization (e.g. hospital admissions) in the year prior to the index date. ✓

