9.7.2 Safety and effectiveness outcomes

The two cohorts (of first-time users of rivaroxaban and first-time users of standard of care) will be followed up from the index date until 12 months after the end of the enrolment period for potential outcomes (safety and effectiveness). For each outcome, the first hospitalization for that outcome during the follow-up period will be identified. A separate follow-up will be performed for each of the outcomes.

For all outcomes (for DVT/PE treatment, SPAF and ACS), crude incidence rates will be estimated in both cohorts, using an as-treated approach. In this, person–time will be categorized into current, recent, past and non use. Current use will refer to person–time up to 7 days after the end of supply of the index drug, recent use will refer to person–time up to 90 days after the end of current use, past use will include all person–time contribution after the end of recent use up to 1 year after the end of current use, non-use will include all remaining time person–time contribution after past-use until end of follow-up.

Age- and sex-adjusted rate ratios with 95% CIs will be estimated for each of the three adverse outcomes comparing rivaroxaban with standard of care using Poisson regression analysis. Where numbers and data permit, adjustment will be made for relevant co-medication (described in the drug utilization section), indication and previous hospitalization for bleeding.

As a general strategy, no data imputation strategies will be applied to supplement missing data. The requirement for inclusion is complete data for critical variables such as exposure to rivaroxaban or standard of care and hospitalizations for bleedings or any other outcome event; otherwise this individual is not eligible to be a member of the study population. However, missing values may occur for potential confounder or effect modifying variables. In this case, individuals with missing values will be kept in the analysis and a separate category will be created for missing values of that variable. In sub-analyses to evaluate confounding or effect modification by variables with a large proportion of missing values, the evaluation will be considered to be conducted on the subset with complete data for the variable of interest.

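### Cardiovascular comorbidity diagnoses are missing from the variable list (9.3.1) and from the adjustment set (9.7.2) for the three bleeding rate ratios, and the cardiovascular subgroup in 8.2 has no variable to support it

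*Protocol*

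**What the plan says.** - **Objective (8.2).** Safety and effectiveness are to be analysed in three special populations: decreased renal function, the elderly, and "patients with cardiovascular comorbidities e.g. hypertension or diabetes".
- **Variable list (9.3.1).** It is introduced with "The following characteristics, including risk factors/potential confounders for the outcomes under study, will be presented for comparison between the two cohorts". Its clinical items are the "diagnosis associated with the prescribing of the index drug", "renal status (estimated glomerular filtration rate [eGFR] or creatinine clearance [CrCl] to be obtained where available", smoking, BMI, bleeding admissions in the prior year and healthcare utilization. Cardiovascular disease appears only as drug classes: antiplatelets, anticoagulants and "antiarrhythmic drugs, antihypertensive drugs, statins, anti-diabetic agents".
- **Adjustment (9.7.2).** Age- and sex-adjusted Poisson rate ratios are planned for the three adverse outcomes, which the abstract identifies as the primary ones: intracranial, gastrointestinal and urogenital bleeding. Where numbers and data permit, "adjustment will be made for relevant co-medication (described in the drug utilization section), indication and previous hospitalization for bleeding".
- **Renal subgroup (9.7.2.1 and Annex 3, Table 12).** This one has an ICD-9-CM code list, four category rules and a planned set of crude incidences.
- **Background (7).** The atrial fibrillation indication applies to patients "with one or more risk factors, such as congestive heart failure, hypertension", older age, diabetes, or prior stroke or TIA.

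**The concern.** Patients are not randomised, and new users of rivaroxaban may differ from new users of standard of care in cardiovascular history. Suppose they do, and suppose that history affects bleeding. A ratio adjusted for age and sex then mixes the drug contrast with the difference in patients. Co-medication can take up part of this, but only conditionally. Drug classes are also indirect markers: antihypertensives are dispensed for several cardiac conditions, and no listed drug class identifies a prior stroke.

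The protocol's safeguard in 9.7.2.2 is to let the patient-characteristics data reveal unexpected biases and then account for them. A condition missing from that list can be seen there only indirectly. Separately, one of the three subgroups in 8.2 has nothing on the list from which its members could be identified by diagnosis.

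**Working it through.** **1. Objective, list and model side by side**

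| Item | Diagnosis in 9.3.1 | In 9.7.2 adjustment | Code list in Annex 3 |
|---|---|---|---|
| Heart failure | no | no | no |
| Ischaemic heart disease | only as ACS indication | only via indication | MI, as an outcome |
| Prior stroke or TIA | no | no | stroke/TIA, as an outcome |
| Hypertension, diabetes | no (drug classes only) | only via co-medication | only renal complications, in Table 12 |
| Renal status | yes | no | yes (Table 12) |
| Prior bleeding admission | yes | yes, conditional | yes |

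The ENCePP checklist (Annex 2) ticks co-morbidity (4.2.5) and known confounders (7.1). For cardiovascular disease the list does not bear this out.

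**2. Could the data supply the diagnoses?** Section 9.4 says the outpatient pharmacy database is fully linked to the national discharge register. Section 9.7.2.1 already uses discharge diagnoses from before the index date for renal disease. The source therefore exists for both arms.

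**3. The plan's own figure.** Section 9.5 gives 5 per 1000 person-years, 12,000 and 48,000 person-years, a ratio of 1.5 to exclude, and 80% power. The type I error is not stated; I assume two-sided 5%.

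Events needed = (1.96 + 0.84)² / (0.2 × 0.8 × (ln 1.5)²) = 299.

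299 / 0.005 = 59,800 person-years, against the stated 60,000. With 60 + 240 = 300 events, power is 80.2%. The figure reproduces and does not depend on this point. It serves below only as a yardstick, and it was set for haemorrhagic stroke alone.

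**4. Illustrative bias.** For one unadjusted binary comorbidity with prevalence p1 (rivaroxaban) and p0 (comparator) and rate ratio k, the bias factor is

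b = (1 + p1(k − 1)) / (1 + p0(k − 1)).

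All p and k are assumptions; the protocol gives none. Using the 60 and 240 events of step 3:

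- Power to exclude 1.5 when the true ratio is 1: Φ[(ln 1.5 − ln b)/√(1/(60b) + 1/240) − 1.96].
- Chance of wrongly excluding 1.5 when the true ratio is 1.5: Φ[−ln b/√(1/(90b) + 1/240) − 1.96].

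| k | More comorbidity on rivaroxaban (p1 vs p0) | b | Power (80% if b = 1) | Less comorbidity on rivaroxaban (p1 vs p0) | b | False exclusion (2.5% if b = 1) |
|---|---|---|---|---|---|---|
| 1.5 | 30% vs 20% | 1.15/1.10 = 1.05 | 72% | 20% vs 30% | 0.96 | 5% |
| 1.5 | 40% vs 20% | 1.20/1.10 = 1.09 | 63% | 20% vs 40% | 0.92 | 10% |
| 2 | 30% vs 20% | 1.30/1.20 = 1.08 | 64% | 20% vs 30% | 0.92 | 9% |
| 2 | 40% vs 20% | 1.40/1.20 = 1.17 | 46% | 20% vs 40% | 0.86 | 22% |
| 3 | 30% vs 20% | 1.60/1.40 = 1.14 | 51% | 20% vs 30% | 0.88 | 18% |
| 3 | 40% vs 20% | 1.80/1.40 = 1.29 | 22% | 20% vs 40% | 0.78 | 46% |

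These factors give no credit for age, co-medication or indication, all of which correlate with the conditions, so they are upper bounds in spirit. Factors for several correlated conditions should not be multiplied together.

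**The case against.** The best defence is that the plan is not blind to these conditions. Age is always adjusted for. Antihypertensive and anti-diabetic use may enter as co-medication. Section 9.7.2 foresees sub-analyses of confounding and effect modification, 9.7.2.2 allows for biases found later, and 9.9 admits unmeasured confounding. Operational subgroup definitions often sit in a SAP, which is not at hand. Discharge records also have limits: 9.9 says that recording secondary diagnoses is not mandatory, so chronic hypertension may be poorly captured.

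Much of this stands, and it limits the point. Four stronger readings are tempting, and the text does not support them:

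- *All comorbidity is absent.* It is not. Renal status and prior bleeding admissions are listed, and the latter is in the conditional adjustment set.
- *The cardiovascular subgroup will be defined by drugs.* The protocol does not say so. It leaves the subgroup undefined; drug classes are merely the only related items listed.
- *Adjusted ratios for stroke and death are biased in favour of rivaroxaban.* Adjusted ratios are planned only for the three bleeding outcomes, and nothing in the protocol fixes the direction of any imbalance.
- *Section 7 names these conditions as bleeding confounders.* It names them as criteria of the atrial fibrillation indication.

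The defence does not remove the core. The protocol itself writes out the confounder list and the adjustment set, and both fall short of its own objective. The unmeasured confounders that 9.9 gives as examples do not include cardiovascular comorbidity.

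**Conclusion.** The point holds for cardiovascular comorbidity diagnoses and the three primary bleeding comparisons. As written, those ratios can reflect heart failure, ischaemic heart disease, prior stroke or TIA, hypertension and diabetes only through age and, conditionally, co-medication and indication. Renal status is collected and classified but not adjusted for. The cardiovascular subgroup lacks the supporting variable that the renal subgroup has.

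On the assumed inputs, one such condition shifts the ratio by a factor of 0.78 to 1.29 before partial correction. The actual size and direction are unknown from the documents. In a study sized to exclude a 50% increase, even the middle of that range matters in both directions: it can hide an excess or cost the study its power. The change should be made, although the omission does not by itself invalidate the design.

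**What to change.** 1. Add to 9.3.1, with code lists in Annex 3, discharge diagnoses from before the index date for heart failure, ischaemic heart disease, prior stroke or TIA, hypertension, diabetes, cancer, liver disease and anaemia. Take them from the linked discharge register in both arms, with the same look-back.
2. Add these and the four-level renal category of 9.7.2.1 to the Poisson model for the three bleeding outcomes. That is 8 + 3 = 11 extra terms, or about 27 planned events per added term if the 300 events of Section 9.5 are reached. If events are few, use a propensity score instead.
3. Define the hypertension and diabetes subgroups of 8.2 from a discharge diagnosis or relevant dispensing, because secondary diagnoses are incompletely recorded.
4. Use GP diagnoses only in a sensitivity analysis restricted to GP-linked patients in both arms. The main analysis takes the full rivaroxaban cohort but only GP-linked comparators (9.2), so GP data would be more complete in one arm.

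Cost: a code list, extra programming on data already linked, and slightly wider intervals. Incomplete recording will leave some residual confounding, which 9.9 should state.
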